17. DATA ANALYSIS PLAN

The primary outcome (receipt of 1+ COVID vaccine) is binary and our main explanatory variable will be an indicator for study arm. We will employ intent-to-treat analyses using generalized linear mixed models (GLMMs) with practice random effects, an approach recommended for group-randomized RCTs in which the goal is to estimate the causal effects of interventions on individuals, adjusted for clustering within groups. This method performs well in situations where the number of observations per cluster is large and for unequal cluster sizes. Models will assume a binomial distribution and a log link function in order to compare vaccination rates between study arms in terms of risk ratios. We will adjust for all practice-level variables included in the randomization balancing criterion, as well as patient-level race/ethnicity. Hypothesis tests will be two-sided with alpha = 0.05. Analyses will be performed

using SAS v. 9.4 (SAS Institute Inc., Cary, NC).

Power Analysis: We conservatively assume a control group vaccination rate of 50% (maximum variance). Adjusting for clustering of patients in practices, and assuming an intraclass correlation (ICC) of 1% (consistent with previous work), this sample size provides 80% power to detect an overall increase of 8.0 percentage point increase in vaccination rates between the QI intervention and control arms. This assumes a chi-squared test (a simplification of the planned mixed model analysis described above), an alpha of 0.05, and a sample size of 5,000 pregnant women organized into 16 practices per study arm.

Final Time/Cost Analysis:

Our two-fold cost measures are (a) total intervention cost to implement the VAX-MOM COVID program aggregated at the three health-system level under a cost analysis and (b) cost per additional COVID vaccination under a subsequent cost-effectiveness analysis. To derive a policy implication regarding the sustainability of programs, we will estimate costs and ICER estimates from the health system perspective.

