Costs: To make these cost measures comparable to similar past interventions of reminders and educational programs, we will estimate cost with one-year time horizon, excluding the cost to purchase, store and administer vaccines. We will estimate the total intervention cost, summing non-personnel costs (e.g., EHR hardware, software, and materials) and personnel costs. The personnel costs will distinguish research costs from intervention costs (e.g., practice-level meeting and collecting EHR data). The dollar values of these personnel costs will be calculated by multiplying “time efforts” (weekly reported by study personnel using a REDCap email survey) with the nationally representative “hourly-wage rates” by occupation codes of study personnel, derived from the Bureau of Labor Statistics. We are using this method in an NIH-funded R01 study (the STOP-HPV study) which involves a practice-level intervention to raise HPV vaccination rates and in the original VAX-MOM study; surveys take <1 minute to complete.

Cost-Effectiveness: We will develop a standard decision model for our cost-effectiveness analyses as conducted in our past studies. The effectiveness measures are the rates of COVID vaccination estimated under Aim 2b. We will estimate incremental cost effectiveness ratios (ICERs) for the intervention defined as: $ICER (Study \text{ vs } control) = (cost_{Study} - cost_{Control}) / (COVID \text{ vaccine rate}_{Study} - COVID \text{ vaccine rate}_{Control})$

In the numerator of the equation, the $cost_{Study}$ is standardized to be equal to average intervention cost per patient in a study arm to account for the potential sample size difference between study and control arms.

As explained above, this intervention cost will exclude the cost to purchase, store and administer vaccines, which is assumed to be identical among all practices. Applying the same assumption, the average cost for the control group ($cost_{Control}$) is zero. Using the developed standard decision model, we will conduct probabilistic analyses to generate point estimates and 95% CIs for ICERs and one-way sensitivity analyses to determine conditions for being lower than the thresholds of cost-effectiveness, e.g., healthcare-system based quality improvement

interventions to improve flu vaccination uptake targeting general populations (median ICER \$51 among 23 interventions) and healthcare workers (median ICER \$125 among 6 interventions) reported by a systematic review.

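### The 95% CI for the ICER, and its comparison with cost thresholds, are not restricted to a positive rate difference, so neither can be interpreted when the effect on vaccination is uncertain

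*Combined protocol and SAP*

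**What the plan says.** Section 17 of the combined protocol and SAP (Cost-Effectiveness) defines the ICER as the cost difference between arms divided by the difference in COVID vaccination rates, study minus control. The study-arm cost "is standardized to be equal to average intervention cost per patient in a study arm". For the comparator the text reads "Applying the same assumption, the average cost for the control group", and the value given is zero. Uncertainty is to be handled by "probabilistic analyses to generate point estimates and 95% CIs for ICERs and one-way sensitivity analyses to determine conditions for being lower than" cost-effectiveness thresholds. Two are offered as examples, both medians from a review of flu vaccination programs: $51 for general populations and $125 for healthcare workers.

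The section does not say what happens if the rate difference is zero or negative. It mentions no dominance convention, net benefit or acceptability curve, and does not make the analysis depend on the primary result. A standard decision model is mentioned but not described. The only statement that fixes the precision of the denominator is in the power paragraph of the same section: "80% power to detect an overall increase of 8.0 percentage point increase in vaccination rates".

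**The concern.** The numerator is the intervention cost per patient less zero, so it is positive whenever the program costs anything. The sign of the ICER is then the sign of the rate difference. Small positive differences send the ratio towards plus infinity and small negative ones towards minus infinity, although the two situations are almost the same. An interval laid along that scale does not run from better to worse. A search for conditions in which the ICER lies below a threshold also picks up every negative rate difference unless these are excluded.

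The plan intends these estimates to inform policy on whether such programs can be sustained. The reported uncertainty therefore has to stay readable when the vaccination effect is small or unclear.

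**Working it through.** **Inputs.** From section 17: control cost 0; two-sided alpha 0.05; control rate 50%; ICC 0.01; 5,000 women; 16 practices per arm; 80% power at 8.0 points; example thresholds $51 and $125. The documents give no cost per patient, so $5 is assumed, with a range of $2 to $10.

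**The plan's own power figure.** The design effect is 1 + (m - 1) x ICC.
- 5,000 women in total, 16 practices per arm: m = 156.25, design effect 2.55, effective n = 2,500/2.55 = 979 per arm. Power for 50% vs 58% is about 94.5%, and the difference detectable with 80% power is 6.3 points. The stated figure is not reproduced.
- 5,000 women in 16 practices in total (8 per arm): m = 312.5, design effect 4.12, effective n = 607.5 per arm, power about 80%. This reproduces it.

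The practice count needs reconciling as a separate matter. Here both readings are carried as a range for the SE of the rate difference: 6.3/2.8 = 2.25 points and 8.0/2.8 = 2.86 points, where 2.8 = 1.96 + 0.84. Reading the text as 5,000 women per arm gives 97.7% power, so the problem would be rarer but the same in kind.

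**How often the CI for the difference includes zero.** The probability is Phi(1.96 - delta/SE).
- True 8 points: Phi(1.96 - 3.56) = 5.5%; Phi(1.96 - 2.80) = 20%.
- True 4 points: Phi(1.96 - 1.78) = 57%; Phi(1.96 - 1.40) = 71%.

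**Point values at $5.** +8 points gives 5/0.08 = $62.5; +2 points gives $250; -2 points gives -$250.

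**Percentile interval at an estimate of +3 points.** Take the difference as normal with mean m = 0.03 and SE s, and the cost c as fixed. For x < 0, P(ICER <= x) = Phi(-m/s) - Phi((c/x - m)/s). For x > 0, add 1 to the right-hand side.

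With s = 0.0225, Phi(-m/s) = Phi(-1.333) = 0.0912.
- Lower limit: Phi((c/x - m)/s) = 0.0912 - 0.025 = 0.0662, so c/x = 0.03 - 1.505 x 0.0225 = -0.00386 and x is about -$1,300.
- Upper limit: Phi((c/x - m)/s) = 1.0912 - 0.975 = 0.1162, so c/x = 0.03 - 1.194 x 0.0225 = 0.00313 and x is about +$1,600.

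With s = 0.0286 the same steps give about -$1,510 and +$1,700. The limits scale with cost: at s = 0.0225 they are about -$520 to +$640 for $2 and -$2,590 to +$3,190 for $10.

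**What that interval contains.** Converted back at $5 and s = 0.0225, it leaves out only rate differences between about -0.39 and +0.31 points. It keeps every larger difference in either direction, however extreme. The 95% CI for the difference itself is 3 +/- 1.96 x 2.25, or -1.4 to +7.4 points. The ratio interval therefore drops values near zero, which are plausible, and keeps values that the data rule out.

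**Threshold comparison.** At $5 the ICER is below $125 when the difference exceeds 5/125 = 4.0 points, and below $51 when it exceeds 5/51 = 9.8 points. It is also below both for any difference under zero. A one-way analysis that varies the difference over -1.4 to +7.4 points would therefore return two separate regions for $125, one of them consisting of worse outcomes.

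**When the effect is clear.** At an estimate of +8 points and $5, the same formulas give $40 to $139 (s = 0.0225) or $36 to $199 (s = 0.0286), which are ordinary usable intervals. Judging by ratio or by net benefit then gives the same share of draws below $51 (21.1% each, s about 0.0226).

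**The case against.** A reader might infer that the plan contains a rule under which a harmful program passes as cost-effective. The documents do not support that. The below-threshold comparison is attached to the one-way sensitivity analyses, not to the simulated draws. The plan never counts draws below a threshold and states no pass/fail test, and $51 and $125 are introduced as examples. A sensible analyst would recognise a costlier, less effective result as dominated. A small positive difference gives a large point ICER that correctly lies above the thresholds. An actual negative estimate is uncommon: 0.02% to 0.26% at a true 8 points, and 3.8% to 8.1% at a true 4 points. All of this stands, and it limits the point to the interval and to the unrestricted comparison.

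It is also true that the plan does not name percentile limits, and that its decision model is not described. This helps less. A dominance label applies to a point estimate and does not repair an interval. A Fieller set also ceases to be an ordinary finite interval once the CI for the denominator includes zero. Some rule is therefore needed whichever method is used.

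Cost per additional vaccination is the plan's chosen measure, for comparability with past programs, and that is a fair reason to keep it as the point estimate. The primary model already handles clustering by practice, and nothing suggests that the cost analysis would drop it.

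**Conclusion.** The point holds as a fault in the planned interval and in a threshold comparison that is not limited to positive rate differences. The sign problem follows from the plan's own definition and does not depend on the assumed cost; only the dollar size of the limits does. The frequencies rest on a normal approximation and on the SE range of 2.25 to 2.86 points taken from the power paragraph. If the true effect is near the planned 8 points, the analysis will usually be sound. If it is nearer 4 points, an uninterpretable ICER interval is more likely than not. Only the cost-effectiveness analysis is affected; the primary vaccination comparison is not. The change should be made before the cost data are analysed.

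**What to change.** Amend the Cost-Effectiveness text in section 17 as follows.

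1. Keep the ICER as the point measure. Where the estimated rate difference is zero or negative, report the program as dominated instead of giving a ratio.
2. Express uncertainty and the threshold comparison as incremental net benefit, lambda x (rate difference) - cost per patient, with a 95% CI. Add an acceptability curve over a range of lambda, marking $51 and $125. In the example above (+3 points, $5 fixed, SE 2.25), net benefit at $51 is 1.53 - 5 = -$3.47, with CI half-width 1.96 x 51 x 0.0225 = 2.25, so -$5.72 to -$1.22. At $125 it is 3.75 - 5 = -$1.25, half-width 5.51, so -$6.76 to +$4.26. Both intervals are finite and run from worse to better.
3. Quote an ICER interval (for example Fieller) only where the 95% CI for the rate difference excludes zero. Net benefit is reported in every case, so no result is withheld by this condition.
4. In the one-way analyses, state threshold conditions for positive rate differences only.

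The cost is a few sentences in the plan and a few lines of code on the same simulation output. The drawback is that no single ICER interval is quoted when the effect is uncertain.
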